Following randomization, participants remain on the run-in diet until the run-in period ends. Participants are not told to which group they have been assigned and, except for staff involved in meal preparation, clinic personnel are also blinded to intervention assignment. Blinding is discussed further in section 16 (Quality Control and Data Management).

Randomization is stratified by clinic and, within each clinic, structured to assure comparable treatment group sizes over time with respect to both dietary pattern assignment and the sequence in which the sodium levels are administered. Although randomization is not stratified by gender, race, or baseline hypertensive status, the distribution of these factors across the treatment groups is monitored to assure that a balanced distribution is achieved.

8. Intervention

The total three-month intervention period is divided into three separate one month (30 day) feeding periods, each at a different level of sodium intake. For each participant, the underlying dietary pattern, control or combination, is the same for all three 30-day intervention feeding periods.

Feeding Breaks

The initial intervention feeding period begins from 0-3 days after the scheduled end of run-in feeding. This could therefore be anywhere from 12-17 days from the start of run-in feeding. Subsequent intervention feeding periods may be separated by breaks of up to 5 days in duration. These breaks are not mandatory, and their duration may vary from site-to-site, and from cohort-to-cohort. Within a given cohort at a given site, however, all participants follow the same feeding schedule. During the breaks between feeding periods, participants are not provided any food and are allowed to return to their original diets. No specific guidelines are provided to participants for what they should eat during these breaks in feeding.

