The breaks between feeding periods are intended to serve several purposes. First, it is hoped that they will boost overall adherence to the feeding regimen and retention in the trial by breaking the overall feeding period (total of 102-104 days) into a series of smaller feeding intervals with which the participants can better comply. Second, the breaks provide the clinical centers with some flexibility in scheduling that should minimize the need to feed participants over major holidays, when compliance is most at risk. And finally, the breaks should help minimize the fatigue factor for clinical center staff and should also allow them to restock food supplies in a less rushed atmosphere.

The breaks between feeding periods are not intended as "washout" periods. In a drug trial, such intervals truly can, in many cases, permit washout of the experimental agent from a participant's system, thus minimizing the likelihood of carryover effects. The potential for carryover effects is unavoidable in this trial, however, since the experimental agent is one's diet and participants must eat something during these intervals. If anything, using breaks between the three intervention feeding periods is likely to increase the variability of response somewhat, since the foods consumed during these breaks can and will vary arbitrarily from person to person.

Ultimately the real issue is not washout, but how long the intervention feeding periods need to be for whatever carryover effects are present to become negligible. The experience from the DASH trial (7) suggests that the impact of the dietary patterns on blood pressure (at least in the context of a controlled feeding trial and at sodium levels comparable to those used in the DASH2 higher sodium diets) is achieved very quickly (within two weeks), so that even if carryover is an issue, its effect is likely to be minimal for blood pressure measurements taken during the final 9 days of intervention feeding.

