During each intervention feeding period participants receive all of their food from the clinic and eat at least one on-site meal per day, five days per week. As with the run-in feeding, the on-site meal should, if possible, be lunch or dinner.

Weight is recorded at each clinic visit during the intervention feeding periods. Blood pressure is assessed weekly during the first three weeks of each intervention feeding period. Five blood pressure measurements are recorded during the final nine days of each intervention feeding period, and at least two of these must occur during the final four days of feeding. All blood pressure assessments consist of a set of two random zero measurements. A 24-hour ABPM reading is also recorded during the final nine days of each intervention feeding period. Additional intervention measurements taken during the last nine days of intervention feeding include: a 24-hour urine (for analysis of Na, K, Ca, phosphorus, urea nitrogen, and creatinine for group analyses) and a fasting blood collection for measurement of lipid levels. Fasting blood samples are also obtained for renin determination, but only the samples obtained during the lower sodium level feeding period are actually analyzed. (The other samples are collected to preserve blinding among clinic staff.) Samples of urine, serum, and plasma, will be frozen and stored for future analysis. Medication use and symptom monitoring, an anonymous compliance survey, and a brief assessment of physical activity occur during the final seven days of each intervention feeding period.

All randomized participants complete an evaluation at the end of the third intervention feeding period summarizing their overall experience with the trial.

The average of all weight measurements recorded during run-in feeding plus the weight taken at SV3 defines the participant's *baseline* weight and is used as the baseline against which to measure weight change during intervention feeding. The overall caloric content of each participant's meals is adjusted as needed in order to assure that weight remains stable during intervention feeding.

Participants may discontinue feeding during a given feeding period provided that all of their measurements are complete and that the resulting break does not exceed the limits set above (i.e., two days following run-in and five days otherwise).

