The primary outcome for the study is the mean SBP at the end of each intervention feeding period. Baseline SBP will be used as a covariate in some analyses. These terms are defined below.

Mean end-of-intervention SBP— the average of the five mean daily SBP measurements recorded during the final nine days of each intervention feeding period. In the event that five sets of final blood pressure measurements are not available, the end-of-intervention SBP is computed as the average of all mean daily SBP readings (minimum of two) recorded during the

final nine days of intervention feeding. For participants who need to start on antihypertensive medications during the feeding period, every effort is made to collect five sets of two daily blood pressures prior to the onset of therapy, and these measurements are used to calculate the end-of-intervention blood pressure for that sodium level. However, participants are not asked to delay the start of clinically indicated medications. For all other participants who terminate their participation prior to the completion of a specific intervention feeding period, their end-of-intervention blood pressures are calculated using the last blood pressure measurement recorded during that feeding period and all other blood pressure measurements recorded within seven days of that measurement. In all cases, the end-of-intervention SBP is computed as the average of the mean daily SBPs.

Once intervention feeding has begun, participants are considered to be in the trial regardless of their actual compliance to the intervention feeding or measurement schedule. Randomized participants who must discontinue participation due to medical reasons (see section 13, Safety Monitoring) and individuals who elect to drop out of the study prematurely are still considered to be in the trial for analysis purposes. For participants who start intervention feeding but have no blood pressure measurements for a given intervention feeding period, their end-of-intervention SBPs for that feeding period are defined to be the average of their mean SV1, SV2, and SV3 SBPs. The rationale for this rule is that participants who drop out of the study are likely to revert to their usual diets, and their screening blood pressures provide our best estimate of what their blood pressure is on their usual diets.

Baseline SBP—the average of all mean daily SBP measurements taken during screening (SV1-SV3) and run-in (i.e., measurements taken on five days).

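### The early-termination rule for end-of-period SBP does not confine its seven-day window to the same feeding period, so a first-week stopper's value can include readings from the previous sodium level or from run-in

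*Protocol*

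**What the plan says.** Section 12 (Primary Outcome) derives the end-of-intervention SBP differently according to what was measured:

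- **Usual case.** The average of the daily means in the "final nine days of intervention feeding", with a minimum of two when the planned five are not all available.
- **Early termination, other than for starting antihypertensive medication.** The value is "calculated using the last blood pressure measurement recorded during that feeding period", together with "all other blood pressure measurements recorded within seven days of that measurement".
- **No reading at all in the period.** The mean of the screening pressures.

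Weighting is equal: "In all cases, the end-of-intervention SBP is computed as the average of the mean daily SBPs".

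Section 8 (Feeding Breaks) allows up to five days between sodium periods and adds that "These breaks are not mandatory, and their duration may vary from site-to-site, and from cohort-to-cohort". The gap between run-in and the first period is 0 to 3 days. Section 8 (Procedures) sets the measurement schedule: "Blood pressure is assessed weekly during the first three weeks of each intervention feeding period". Five assessments follow in the last nine days, and "at least two of these must occur during the final four days of feeding". Run-in uses the control diet at the higher sodium level for everyone, with blood pressure taken weekly (section 7).

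**The concern.** In the early-termination sentence, the restriction to the feeding period attaches to the last reading only. The other readings are selected by calendar distance alone, and no other section adds a limit; the missing-data text in section 14 simply refers back to section 12. Breaks can be absent and readings are densest at the end of each period, so a participant who stops soon after a switch has the previous level's final readings inside the window.

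A programmer following the sentence would average them in and label the result with the new sodium level. In the first period the window can reach a run-in reading, which is control diet at higher sodium even for a combination-diet participant.

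This matters because the design has no washout. Section 8 argues that the effect of the dietary patterns "is achieved very quickly (within two weeks), so that even if carryover is an issue", it should be minimal for readings in the final nine days. Section 14 (Aim #1) makes absence of carry-over a basic assumption of the primary analysis. A value that averages across two periods lacks that protection. A single first-week reading is also enough to switch off the screening-mean rule, which applies only when the period has no reading.

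**Working it through.** **1. The plan's own figure.** Section 15 gives Aim #1 detectable effects of 0.8, 0.9 and 1.0 mm Hg at 70%, 80% and 90% power. Inputs from sections 14 and 15: within-person variance 40, five readings per value, 200 participants per diet, two-sided 0.05 with Holm for two tests (first step 0.025).

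- SE = √(2 × (40/5) / 200) = 0.283 mm Hg.
- Detectable effect = (2.241 + z for the power) × 0.283 = 0.78, 0.87 and 1.00.

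This matches the table. The figure is not disputed; it is used below to express the size of the effect.

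**2. When the window crosses into the previous period.** Let b be the gap in days and d the day of the last reading in the new period. Day 30 of the previous period lies b + d days earlier. The seven-day look-back therefore covers 8 − b − d days of the previous period when b + d ≤ 7, and none otherwise.

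| Gap b | d = 1 | 2 | 3 | 4 | 5 | 6 | 7 |
|---|---|---|---|---|---|---|---|
| 0 | 7 | 6 | 5 | 4 | 3 | 2 | 1 |
| 3 | 4 | 3 | 2 | 1 | 0 | 0 | 0 |
| 5 | 2 | 1 | 0 | 0 | 0 | 0 | 0 |

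The rows for gaps 0 and 3 also apply between run-in and the first period. When b + d ≤ 4, the whole of the previous period's last four days is covered, so its minimum of two readings must enter.

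**3. Weight of the earlier readings.** With k earlier readings and one current reading, the earlier ones carry k/(k + 1): 50% for one, 67% for two, 75% for three, 83% for five. One run-in reading joined to one first-period reading carries 50%.

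**4. Example.** No break, one reading on day 3, then withdrawal. The window reaches back to day 26. At least two readings fall in days 27 to 30, and at most all five fall in days 26 to 30. The previous level supplies 2/3 (67%) to 5/6 (83%) of the value. If the true difference for that person were 5 mm Hg (an illustrative assumption) and the day-3 reading already showed all of it, the recorded difference from the previous level would be 5 × 1/3 = 1.7 down to 5 × 1/6 = 0.8 mm Hg.

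**5. Trial level.** Let f be the share of participants for whom one value in a contrast is mixed with the other level in that contrast, at weight w. The contrast is multiplied by 1 − f·w. The protocol does not give f, so a range is assumed, with w from 50% to 83%. Power for a true 1.0 mm Hg is Φ(multiplier/0.283 − 2.241), which is about 90% with no mixing.

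| Assumed f | Multiplier | Power at 1.0 mm Hg |
|---|---|---|
| 1% | 0.995 to 0.992 | about 90% |
| 5% | 0.975 to 0.958 | 89% to 87% |
| 10% | 0.950 to 0.917 | 87% to 84% |

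**The case against.** **The sentence may simply be loose.** It defines the value for one particular feeding period, and the neighbouring rules are all per period, so the authors may well have meant the window to stay inside it. That is plausible, but the limit is not written anywhere. This is the operative definition of the primary outcome.

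**The situation is narrow.** Mixing needs a last reading in about the first week; after a five-day break, only on day 1 or 2. The 83% end also needs all five earlier readings packed into five days. This stands and limits the size. Even the 10% worst case would turn the 3 mm Hg reference value of section 15 into 3 × 0.917 = 2.75 mm Hg, more than nine standard errors of 0.283.

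**Carry-over has a planned check.** Section 14 (Aim #1) fits an exponential carry-over model. It is reported to help interpretation and does not change how the primary value is derived, so it does not repair the rule.

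**Early readings are used on purpose.** Section 12 keeps everyone who starts feeding in the trial whatever their compliance, and section 14 states an intention-to-treat approach. This stands. A reader might infer that readings from the first two weeks should be barred, for example by a day-15 minimum. The documents do not support that:

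- The two-week figure in section 8 concerns the dietary patterns at sodium comparable to the higher level. It is an upper bound, not an onset time for sodium.
- The fallback in sections 12 and 14 is the screening mean, which is pressure on the usual diet. Section 9 describes the higher sodium level as reflecting current intake. If the previous level in the day-3 example was higher, the recorded difference would fall from 0.8–1.7 mm Hg to about 0.
- Someone whose last reading falls on days 8 to 14 has a window wholly inside the assigned period. A day-15 rule would discard those on-diet readings.

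**Conclusion.** Wrong as written, of minor severity. Taken literally, the early-termination rule can assign to one sodium level a value that comes mostly from another level or from run-in. This happens whenever the gap plus the day of the last reading is 7 or less and the earlier period has readings in the window.

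For the individuals affected the error is large: 50% to 83% of the value in the cases worked above. For the trial it is probably small, about 0.5% to 8% of a contrast with the preceding level if 1% to 10% of participants are affected. Those shares are assumptions.

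A reader might go further and infer that every sodium contrast is pulled toward zero. That does not follow, because the direction depends on which level came before. An intermediate-level value mixed with preceding lower-level readings shrinks the intermediate-versus-lower contrast but widens higher-versus-intermediate. A control-diet participant starting at the higher level draws on an identical run-in diet, so nothing is diluted. Nor does the point show that carry-over affects the primary outcome of participants who complete their periods.

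**What to change.** In section 12 (Primary Outcome), limit the additional readings in the early-termination rule to those recorded during the same feeding period as the last reading, still within seven days of it. Add that readings from run-in or from another feeding period never enter a period's value. The previous-period weight then becomes zero in every case.

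The cost is one phrase, one sentence and a period filter in the derivation program. No participant loses a value, because the last reading of the period always remains.

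Do not add a minimum day on diet to the primary derivation. If early readings are a worry, at most report a sensitivity analysis that omits values resting only on readings from the first two weeks of a period.

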Rationale: Much of the research on the relationship between sodium intake and blood pressure occurs in the upper ranges (i.e., > 50 mmol) of intake. Although some evidence exists for a greater than expected lowering of blood pressure at very low levels of sodium intake, an analysis of INTERSALT data reported that no model fit the data better than a linear model. This specific aim will help fill this knowledge gap.

We hypothesize that the relationship between sodium and blood pressure is not linear, with greater than linear responsiveness at lower levels of sodium. We will test the above four specific aims using RZ-SBP as the primary outcome variable and RZ-DBP and 24-hour SBP as secondary outcome variables.

Other Objectives

We also address the following additional objectives.

- 1. To assess whether the observed effects of both the DASH combination dietary pattern and sodium intake on blood pressure vary according to baseline characteristics such as race, sex, baseline blood pressure, body mass index, waist circumference, education, and diet prior to entry into the study.
- To determine the extent to which age influences blood pressure response to the DASH combination diet and to sodium reduction. Because salt sensitivity increases with age, we would expect age to be an effect modifier for the sodium intervention. Although age had no apparent effect on response to the DASH combination diet, an effect may be present when both the DASH combination diet and sodium reduction are combined.
- 3. To determine the extent to which renin profile influences blood pressure response to the DASH combination diet and sodium reduction.
- 4. To assess the effects of the DASH combination dietary pattern and sodium intake (*Specific Aims 1-4*, above) on selected measures of ambulatory blood pressure, including 24-hour DBP, waking SBP and DBP, and sleeping SBP and DBP. In addition, as exploratory analyses, we will assess these ambulatory pressure indices in the analyses outlined in *Other Objectives* 1-3, above.
- 5. To assess the effect of the DASH combination dietary pattern and sodium intake on dipper/nondipper status (a measure of nocturnal blood pressure decline).

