DASH2 participants also provide a 24-hour ABPM reading during the last nine days of each intervention feeding period. The DASH2 ABPM measurement protocol is adapted from that advocated by the British Hypertension Society and is identical to that used in DASH. Staff obtain both the usual RZ measurements and ABPM readings when the monitor is placed in order to confirm satisfactory readings in the clinic setting. Participants are then asked to wear the device for a full 24-hour period. Upon return to the clinic, the data are downloaded to the computer and checked to confirm that at least 14 acceptable readings were obtained between the hours of 6 a.m. and 12 midnight. If so, the monitoring is deemed acceptable. If fewer than 14 acceptable readings are available during this timespan, the participant is asked to repeat the monitoring.

We will use 24-hour SBP as a secondary outcome analogous to RZ-DBP. Other ambulatory pressure indices, including 24-hour DBP and waking and sleeping pressures, will be used for exploratory analyses. "Waking" and "sleeping" pressures are calculated according to the times of going-to-sleep and awakening indicated by the participants on the day they wear the ambulatory monitor.

Other Outcomes

A standard lipid panel is run on (8-hour) fasting blood samples collected at SV3 and during the last week of each intervention feeding period. Total cholesterol, VLDL-C, HDL-C and triglyceride levels are measured directly, and LDL-C levels are calculated. These data are used to validate differences in dietary consumption between the control and combination diets and also to assess the impact of lower levels of sodium on total and LDL-C cholesterol. All analyses are done centrally, and a minimum fast of eight hours is required for the measurement to be valid.

Plasma renin activity is measured in samples drawn after an overnight fast and at least 90 minutes in the upright position. Samples are collected during the last week of each intervention feeding period, but only the samples corresponding to the lower sodium level diet are analyzed. A minimum fast of eight hours is required for this measurement. Renin level is measured to determine the extent to which renin profile influences blood pressure response to the DASH combination diet and sodium reduction.

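### The only stated check on an ambulatory recording covers 6 a.m. to midnight, so a recording with little or no night data passes for 24-hour SBP

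*Protocol*

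**What the plan says.** Protocol section 12, Secondary Outcomes, describes one 24-hour recording in the last nine days of each intervention feeding period. "Participants are then asked to wear the device for a full 24-hour period". On return, the data are downloaded and "checked to confirm that at least 14 acceptable readings were obtained between the hours of 6 a.m. and 12 midnight". Then: "If so, the monitoring is deemed acceptable". The only trigger for another recording is a shortfall in that count: "If fewer than 14 acceptable readings are available during this timespan, the participant is asked to repeat the monitoring".

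The accepted recording serves several purposes:

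- 24-hour SBP: "We will use 24-hour SBP as a secondary outcome analogous to RZ-DBP". Section 2 names it as a secondary outcome for all four specific aims, and section 14 (Aim #1) extends it to the sex, race and hypertension subgroups.
- Waking and sleeping pressures: "Other ambulatory pressure indices, including 24-hour DBP and waking and sleeping pressures, will be used for exploratory analyses". The two are "calculated according to the times of going-to-sleep and awakening indicated by the participants on the day they wear the ambulatory monitor".
- Nocturnal decline, in section 2, Other Objectives: "To assess the effect of the DASH combination dietary pattern and sodium intake on dipper/nondipper status".

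Section 3 (Ambulatory Blood Pressure Monitoring) notes that pressure typically falls during sleep. It gives the lack of data on salt and sleeping pressure as one reason for monitoring. The ambulatory part of section 16 (Staff Training and Certification) covers training, certification and monitor placement, and sets no overnight minimum.

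**The concern.** The acceptance test does not match the quantities taken from the recording. Wearing the monitor for 24 hours is requested, but it is not part of the test. If the cuff comes off at bedtime or the monitor fails overnight, the recording can still pass and the clinic has no stated reason to repeat it.

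Two consequences follow. If 24-hour SBP is then taken as an unweighted mean, it is too high, because the lower night values are absent. Sleeping pressure and dipper status are either missing or rest on one or two readings, again with no repeat.

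Section 14 states that ambulatory pressure has no baseline measurement, so each participant has one recording per sodium level. If one of these has a night and another does not, the whole overstatement enters that person's sodium difference. A later analysis rule could discard such a recording but could not recover the night once the feeding period has ended.

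**Working it through.** **Coverage of the rule.** The window is 18 of 24 hours; the other 6 hours (6/24 = 25% of the day) carry no requirement. The protocol does not give the reading interval. At assumed intervals of 15, 20, 30 or 60 minutes, 14 readings take 14 x interval / 60 = 3.5, 4.7, 7 or 14 hours. At each of these intervals the rule can be met before midnight and with no sleep readings.

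**Scale reference from the plan.** No detectable effect is given for ambulatory SBP. For clinic SBP, section 15 gives 1.0 mm Hg at 90% power for a sodium contrast within a diet. With within-person variance 40, five days averaged, 200 per diet and a two-test Holm step, SE = sqrt(2 x (40/5)/200) = 0.283. The detectable effect is (2.241 + 1.282) x 0.283 = 1.00, which matches. It is a group contrast for clinic SBP, so it can be set beside a bias in a contrast but not beside an error in one recording.

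**Error in one recording.** Let D be waking minus sleeping SBP and h the hours of sleep. The true 24-hour mean is the waking mean minus D x h/24. An unweighted mean with no sleep readings is therefore too high by D x h/24. D = 10-20 mm Hg and h = 6-8 are assumptions.

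**Added variance.** If a fraction q of recordings lose the night at random, the variance per value rises by q(1 - q) x shift squared. With q = 0.05 (assumed), q(1 - q) = 0.0475.

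**Bias in a contrast.** This is the difference in night-loss rate between conditions x shift, with differences of 5 and 10 percentage points assumed.

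| D (mm Hg) | h | Shift (mm Hg) | Added variance (mm Hg squared) | Bias, 5 points (mm Hg) | Bias, 10 points (mm Hg) |
|---|---|---|---|---|---|
| 10 | 6 | 2.5 | 0.30 | 0.13 | 0.25 |
| 10 | 8 | 3.3 | 0.53 | 0.17 | 0.33 |
| 20 | 6 | 5.0 | 1.19 | 0.25 | 0.50 |
| 20 | 8 | 6.7 | 2.11 | 0.33 | 0.67 |

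**Sensitivity.** Writing the dip as 5-20% of a waking SBP of 130-140 mm Hg (also assumed) widens the shift to between 130 x 0.05 x 6/24 = 1.6 and 140 x 0.20 x 8/24 = 9.3 mm Hg. A 10-point difference in loss then gives a bias of about 0.2-0.9 mm Hg.

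All shifts are for a wholly missing night and an unweighted mean. A partly recorded night gives a smaller shift.

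**The case against.** The strongest reply is that section 12 describes a clinic check for repeating the recording, not the analysis definition. The protocol does not say that 24-hour SBP is a raw mean. The formula and any minimum for analysis could properly sit in an analysis plan or the procedures manual. That stands as far as computation goes: a reader might infer that a daytime mean is analyzed as 24-hour SBP, but the document does not state it. The reply does not reach the accept-or-repeat decision, which the protocol fixes itself and which determines whether night data exist.

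Other points that stand:

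- A reader might infer that a recording with no night counts as a valid sleeping-pressure or dipper recording. It does not: those indices use reported sleep times, so with no sleep readings they are missing rather than falsely valid.
- The window runs by the clock and may include some sleep before midnight or after 6 a.m. None is required.
- A reader might expect fatigue in later periods to bias the sodium contrast. All six sodium orders occur equally at each site and in each diet arm (section 16), and the model includes period effects (section 14), so loss that merely rises with period is not confounded with sodium.
- Nothing in the document shows that night loss differs by sodium level or diet.
- The procedure is stated to be the same as in the predecessor trial. That supports comparability, but it does not make a 6 a.m.-to-midnight count a check on 24-hour SBP.

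**Conclusion.** The point holds in limited form. The stated acceptance rule does not fit 24-hour SBP, because a recording with few or no night readings passes and is not repeated.

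The shift in an affected recording could be several mm Hg, but only if the mean is unweighted. Night loss unrelated to treatment adds noise. The contrast is biased only if loss differs by sodium level or diet, and in the main table that bias stays below the 1.0 mm Hg reference even at the extreme. The dip, the sleep duration, the 5% loss and the 5-10 point difference are all assumptions.

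The outcome affected is secondary, tested without multiplicity adjustment. The sleep indices are exploratory or belong to other objectives. The primary outcome, clinic SBP, and the stated sample size and power are unaffected. This is a low-cost improvement that should be made, not a threat to the trial's main conclusion.

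**What to change.** In section 12, Secondary Outcomes:

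1. Keep the 14-reading criterion for waking pressure, which preserves comparability with the predecessor trial.
2. For 24-hour SBP, sleeping pressure and dipper status, also require a prespecified minimum number of readings within the reported sleep interval. The investigators should set the number from the programmed reading interval.
3. When that minimum is not met, use the existing repeat step within the nine-day window.
4. Define 24-hour SBP as the time-weighted mean of the waking and sleeping means.
5. Treat recordings that still fail as missing for the 24-hour and sleep indices; they still contribute to waking pressure.
6. Report completeness of night data by sodium level and diet. Setting failures to missing does not cure treatment-related loss, so readers need to see whether any occurred.

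This version is dated March 1999, within the feeding period of February 1998 to January 2000. The analysis rule should therefore apply to all cohorts, and the repeat rule to the recordings still to come.

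The cost is a wording change in the protocol and manual, a small change to the analysis code, some repeat recordings, and slightly fewer complete 24-hour values.
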